Ceylan et al. (2002)²⁶ evaluated the longitudinal growth changes in the incisor position, overjet, and overbite between 10 and 14 years of age using serial lateral cephalographs. Radiographs of 63 patients were taken at 10, 11, 12, and 14 years old. The results showed age affected the measurements of overbite, upper incisor-NA (mm), lower incisor-NB (mm), upper incisor-NA (angle), and the interincisal angle. Gender affected the overbite, upper incisor-NA (mm), upper incisor-NA (angle) and upper incisor-SN (angle).

Weyrich and Lisson (2009)²⁷ evaluated the effect of premolar extractions on incisor position and soft tissue profile in patients with Class II, Division 1 malocclusion using cephalometry. The concluded that patients who have undergone camouflage treatment exhibit significantly more retruded upper central incisors than those with extractions in both jaws, and that their upper incisors are highly significantly more retruded and their mandibles significantly more retrognathic than those of patients who have not undergone extraction therapy.

Yang and Qian (2016)²⁸ investigated the relationship of torque control and type of dental movement, as well as the relationship between reconstruction of the alveolar bone and retraction of the anterior teeth during anterior segment retraction. Lateral cephalometric radiographs as well as CBCT were used to evaluate the inclination degree of the upper anterior teeth, the horizontal and vertical displacement of edge and apex, and the thickness of the alveolar bone at the apex. The study concluded that, during retraction, cases who received torque control showed less inclination degree change of the upper anterior teeth, less lingual displacement of the edge, more lingual displacement of the apex.

3) 3D digital model scanning and its reliability

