Primary Outcome	Rate of space closure	Digital scanned dental models	
- Scanned digital models in (mm)
○ Models taken every month○ Analysed using 3 Shape Software

Secondary Outcome	Anchorage loss	Digital scanned dental models	Linear measurement in scanned digital models (mm)
	Molar Rotation	Digital scanned dental models	Degrees
	Vertical position	Lateral Cephalometric Xray	Mm
	Torque of anterior teeth	Lateral Cephalometric Xray	Degrees
	Pain	Pain scoring sheets given to patients	VAS scoring from 1-10 ^(Fig 1)

B-Research question:

In orthodontic patients with maxillary protrusion, can frictionless mechanics offer a faster rate of retraction compared to frictional mechanics?

Objectives of the study

Research hypothesis:

The null hypothesis (H_0) of this research is that there's no difference between both frictionless and friction mechanics on rate of retraction during en-masse retraction following 1st premolar extraction.

Primary objective:

Evaluating the rate of En-masse retraction using frictionless vs friction mechanics.

Secondary objectives:

Assessing the amount of anchorage loss, root resorption, pain and discomfort during retraction. In addition to this, changes in vertical position (extrusion/ intrusion), tip and torque of anterior teeth will be measured following en-masse retraction using frictionless vs friction mechanics.

Study design:

This is a randomized clinical trial with two arms parallel group, and 1:1 allocation ratio. In one group, frictionless mechanics will be applied during en-masse retraction, while the other group will receive frictional mechanics. The rate of retraction will then be compared between both interventions.

Material and Methods

I) Participants, Interventions, and Outcomes

A] Study Setting:

The study will be performed in the clinic of the Orthodontic Department at the Faculty of Oral and Dental Medicine, Future University. The recruited sample would be from the Egyptian urban and rural population.

B] Eligibility criteria:

- Inclusion criteria:** for the participants include the following:
 1. Adults and Adolescent patients (both genders)
 2. Age range (14-24)
 3. Patients with maxillary protrusion requiring first premolars extraction (Bimaxillary Protrusion or Class II division 1 cases).
 4. Patients with fully erupted permanent teeth (not necessarily including the third molar).
 5. Cases requiring maximum anchorage during retraction.

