Our sample size calculation is based on a previous study comparing the effect of friction and frictionless mechanics²⁴. Using PS software output, we are planning a study of a continuous response variable from independent Group I and Group II subjects with 1 Group I(s) per Group II subject. In a previous study the response within each subject group was normally distributed with standard deviation 0.76. If the true difference in the Group II and Group I means is 1.0, we will need to study 10 Group II subjects and 10 Group I subjects to be able to reject the null hypothesis that the population means of the Group II and Group I are equal with probability (power) 0.8. The Type I error probability associated with this test of this null hypothesis is 0.05. Considering drop out a sample size 15 per group is appropriate.

F] Recruitment strategy:

The principal investigator will recruit the patients from the clinic of Orthodontic department, Faculty of Oral and Dental Medicine - Future University.

Screening of patients will continue until the total number of participants for the study is collected.

II) Assignment of interventions:

A] Sequence generation:

The supervisor of the study will apply Computer generated random numbers to randomly assign patients to group A (Frictionless) or B (friction) using Microsoft Office Excel 2007 sheet. The patient numbers will be written in the first column, and the supervisor will select function RAND() to generate the randomization number in the second column. These numbers will be sorted according to the randomization number so the first column numbers will be randomly distributed.

B] Allocation concealment mechanism:

The supervisor of the study will write the randomization numbers of the patients on opaque white papers folded three times to form sealed envelopes and store it inside a box. The codes for randomization will be securely held at the secretary's office.

C] Implementation:

At the time of intervention, the main operator will send the patient to the secretary's office. Then, the assigned employee will open the box and ask the patient to select one envelope. The main operator will assign each participant for the corresponding intervention either (friction or frictionless group) according to the list of codes of randomization.

Assignment to either intervention will occur before levelling and alignment stage.

D] Blinding:

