Data will include all photographs, models, radiographs and filled questionnaire.

C] Statistical Analysis:

- The principle investigator will be responsible for the extraction of the required data from the CBCT taken before and after retraction as well as the study models taken at every follow up visit. The data will be sent to a specialized statistician.
- The specialized statistician will be responsible for the statistical analysis of the study by:

1. Presenting the data as mean, standard deviation (SD) and Standard error (SE) values.
2. Using Paired t-test to compare between the friction and the frictionless group of retraction as well as to compare between the pre-and post -treatment data for each group.
3. Using Anova test to determine the rate of anterior segment retraction.

4. Statistically evaluate the patient acceptance for both techniques.

- For this study, the specialized statistician will use IBM11 SPSS12 Statistics Version 20 for Windows to perform the required statistics.
- The significance level will be $P \leq 0.05$. Highly significant variables are detected when P value is less than 0.01.

Assessors Reliability:

- To achieve high reliability for measurements, the supervisor will choose a well-experienced inter-examiner during the study.
- A training session will be provided for the examiners to ensure standard measurements techniques.
- Each examiner will complete the measurements on a model and will repeat the procedure after one week to assess the intra- and inter-examiner reliability.
- The supervisor will compare the measurements of the two assessors for disagreement with a difference of more than one millimeter.
- the supervisor will evaluate the amount of variation in measurements among and between examiners to test the performance of each assessor.
- The examiner with less reliability will receive additional training but will be replaced during the study.
- The specialized statistician will calibrate the intra and inter-examiner reliability for the measurements of the study by the Intra-class correlation coefficient (ICC). The closer the ICC to 1.0, the higher reliability between assessors. According to Fleiss: "ICC values between 0.7 and 0.9 represent good reliability." The kappa scores between study examiners will be calculated, a range of 0.60-0.80 will represent acceptable reliability.

IV) Method Monitoring:

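### The T0 value of torque, vertical position and molar rotation is only subtracted, where a model of T1 on arm and T0 would be more precise; age and malocclusion type belong in a sensitivity analysis of the rate

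*Combined protocol and SAP*

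**What the plan says.** **Who is enrolled.** Inclusion criterion 3 admits "Patients with maxillary protrusion requiring first premolars extraction (Bimaxillary Protrusion or Class II division 1 cases"; criterion 2 sets "Age range (14-24" years. The sample size section enrols 15 per group.

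**Randomisation.** Sequence generation uses one spreadsheet list sorted on a random number, and patients draw an envelope from one box. No strata are described. Assignment takes place before levelling and alignment.

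**Records.** A cephalogram (T0) and impressions for digital models are taken for every patient after levelling and just before retraction starts (Interventions, pre-intervention records). Age and malocclusion type must be known to judge eligibility.

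**Analysis.** The Outcomes section assesses all outcomes as the difference between T0 and T1. Statistical Analysis item 2 reads "Using Paired t-test to compare between the friction and the frictionless group of retraction", and the same test is used for pre/post changes within each group. Item 3 names an ANOVA for the rate without giving a factor or covariate. No adjusted analysis is planned.

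**Background.** The cephalometric part of the Literature Review cites a study of Class II division 1 patients in which "patients who have undergone camouflage treatment exhibit significantly more retruded upper central incisors than those with extractions in both jaws". It also cites a study in which age affected upper-incisor measures between 10 and 14 years.

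**The concern.** Thirty patients of two malocclusion types and a ten-year age span are randomised without strata and compared without covariates. Chance imbalance between the arms is then likely, and any variance that baseline data could explain stays in the error term. The review cited in the plan gives some reason to expect incisor measures to depend on such factors.

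The clearest loss concerns the outcomes that have a T0 value. A change score assumes that each unit of T0 carries over fully to T1, a slope of exactly 1. When the correlation is below 1 and the variances are similar, the true slope is smaller, and subtracting all of T0 adds noise. In a trial of this size, that reduces the chance of seeing real differences in torque, vertical position or molar rotation.

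**Working it through.** **1. The plan's own sample size.** Inputs from the sample size section: "If the true difference in the Group II and Group I means is 1.0"; "the response within each subject group was normally distributed with standard deviation 0.76"; power, "with probability (power) 0.8"; alpha, "The Type I error probability associated with this test of this null hypothesis is 0.05". Units and sidedness are not stated; I take two-sided.

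n per arm = 2 × (1.96 + 0.84)² × 0.76² / 1.0² = 9.07, rounded up to 10. The stated figure reproduces. The noncentral t gives power 0.795 at 10 per arm and 0.935 at 15.

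**2. Change score against ANCOVA (torque, vertical position, molar rotation).** Assume variance σ² at both T0 and T1, and within-arm correlation ρ. The documents give neither.

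- Change score: Var(T1 − T0) = 2σ²(1 − ρ)
- ANCOVA residual: Var(T1 given T0) = σ²(1 − ρ²)
- Ratio = (1 − ρ²) / [2(1 − ρ)] = (1 + ρ)/2

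Estimating one slope inflates the variance on average by 1 + 1/(N − 4). With N = 30 this is 1 + 1/26 = 1.038, about 4%.

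| ρ (assumed) | (1 + ρ)/2 | × 1.038 |
|---|---|---|
| 0.3 | 0.65 | 0.675 |
| 0.5 | 0.75 | 0.779 |
| 0.7 | 0.85 | 0.883 |

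The gain disappears only when (1 + ρ)/2 × 1.038 reaches 1, at ρ of about 0.93. Beyond that, the most that can be lost is the 4% and one degree of freedom.

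**3. Imbalance in malocclusion type.** Take arms of 15 and 15, with half the 30 patients of each type (assumed). By the hypergeometric distribution, the chance that the arms differ by 3 or more patients is 0.466, and by 5 or more 0.143. A difference of 5 out of 15 moves the estimate by one third of the true gap between types.

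**4. Adjusting the primary rate for type and age.** R² is the share of outcome variance that the two covariates explain (assumed). The residual SD is 0.76 × √(1 − R²). The variance is inflated by 1 + 2/(N − 5) for chance covariate imbalance, which is 1 + 2/25 = 1.08 at N = 30. Residual degrees of freedom fall from 28 to 26.

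| 15 per arm | Unadjusted | R² = 0 | R² = 0.10 | R² = 0.25 |
|---|---|---|---|---|
| Difference 1.0 (planned) | 0.935 | 0.916 | 0.940 | 0.971 |
| Difference 0.8 (assumed) | 0.795 | 0.761 | 0.804 | 0.869 |

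The break-even R² is about 0.08 with 30 patients. With 10 evaluable per arm, the number on which the plan is powered, the inflation is 1 + 2/15 = 1.133 and the break-even R² is about 0.13. Below these values adjustment lowers power.

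**The case against.** Five points can be made for the plan.

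- **T0 is already used.** It enters every outcome as a change score. This stands: the gain is that of ANCOVA over a change score, not of using T0 over ignoring it.
- **T0 is not a pre-randomisation value.** It follows assignment and levelling, and the unblinded operator takes the impressions. This must be stated in the plan. It does not rule T0 out, because T0 precedes the differing retraction mechanics and the same levelling procedure is described for both arms.
- **No documented link to the primary outcome.** Of the two cited studies, one concerns incisor position by type of treatment, the other changes at ages 10 to 14. As the review reports them, neither addresses the rate of space closure. This stands, and an R² of zero is as compatible with the documents as 0.25.
- **The wrong test comes first.** A paired t-test cannot compare two independent arms. This stands and must be corrected whatever is decided about covariates.
- **Pooling may already be in the SD.** The study on which the sample size is based included Angle Class I and Class II subjects, so 0.76 may already contain variance between types.

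A reader might infer that pooling the two types without stratification biases the comparison, or that adjusting the primary analysis for type and age would cost nothing. The documents support neither. A correct unadjusted test keeps its type I error under randomisation, and at R² = 0 the adjustment costs 1.9 points of power at the planned difference (0.935 − 0.916) and 3.4 at 0.8 (0.795 − 0.761).

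**Conclusion.** The point holds in a limited form and is a minor improvement.

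For torque, vertical position and molar rotation, regressing T1 on arm and T0 is better than the change-score t-test over nearly the whole range of plausible correlations. With 30 patients the net variance reduction is about 32%, 22% and 12% at ρ of 0.3, 0.5 and 0.7, given equal T0 and T1 variances. The documents give no ρ, so the size is conditional, although the direction is secure up to a ρ of about 0.93.

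For the primary rate, adjustment for malocclusion type and age may help or hurt, depending on an undocumented R². It therefore does not belong in the main analysis. Imbalance in type is likely if the types are equally common (47% for 3 or more patients), but it costs precision and ease of interpretation, not validity. The randomisation can stay as it is.

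**What to change.** In the Statistical Analysis section:

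1. Replace the paired t-test between arms with an independent-samples comparison, and make that the main analysis of the rate of space closure.
2. For torque, vertical position and molar rotation, compare the arms with a linear model of the T1 value on arm and the T0 value, in place of the t-test on the T0–T1 difference.
3. State that T0 is recorded after assignment but before the retraction mechanics differ, with the same levelling procedure in both arms.
4. Pre-specify one sensitivity analysis of the rate: a linear model on arm, malocclusion type and age, with no further covariates. Fixing these now prevents adjustments being chosen after an imbalance has been seen.

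The cost is wording only: no new data, visits or patients. The T0 models give up one residual degree of freedom and about 4% of variance with 30 patients. The rate sensitivity model gives up two degrees of freedom and about 8% (factor 1.08), which is why it stays secondary.

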- A ligature wire extended between the second premolars and miniscrews will be used for proper anchorage control.
- Closing retraction T-loops will be fabricated using 0.017 x 0.025 TMA wire. The loop will be positioned halfway the extraction space and the canine.^{35,36}.
- A gable angle of 45° will be added.
- Distal activation of 4 mm will be done with cinch back the wire distal to 2nd molars bilaterally.³⁷

Friction group:

- Crimpable hooks added to the arch wire (0.017"x0.025" Stainless steel) distal to the lateral incisor passing near the center of resistance of the anterior segment.
- Retraction will start on a 0.017"x0.025" Stainless steel wire using elastomeric chain (force applied will be 212 g per side)³⁸ extending between the crimpable hooks and the miniscrew.
- The force will be measured by a force gauge and reactivated every 4 weeks maintaining constant force of retraction all over the retraction phase.

➤ **Follow up visits**

Patients will be asked to attend for follow up sessions every 4 weeks for:

- Evaluation miniscrews stability.
- Replacement of the power chain to maintain a force of 212 gm per side.
- Reactivation of the T-loop by further distal activation and cinch back.
- Impression taking to determine the overall rate of retraction.

➤ **Criteria for discontinuing or modifying the allocated intervention:**

In cases of prolonged swelling or pain related to the miniscrew, the patient will be given strict oral hygiene measures and may wait for three weeks before the beginning of retraction.

In cases of loose or broken miniscrews, the screw will be removed and replace the miniscrew after complete resolution of the inflammation.

□ **Post-retraction Questionnaire:**

The patients of both groups will be asked to fill in questionnaires regarding their experience with their allocated technique

□ **Retraction records**

Following en-masse, patients will be referred to the same radiology center to acquire the final lateral cephalometric x-ray to assess the movement and inclination of anterior teeth.

The final dental model will assess the rate of retraction, molar rotation, and molar anchorage loss achieved throughout the study.

□ **Material Used**

- American Orthodontics Brackets, Roth prescription, 22 slot size.
- American Orthodontics Elastomeric power chains
- American Orthodontics Elastomeric O-ties
- American Orthodontics Ligature wire.

- Jiel Miniscrew, 8 mm TAD
- American Orthodontics Arch wires.

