- American Orthodontics Molar bands/tubes.

D] Outcomes

[figure not shown]
Primary outcome: is to monitor the rate of space closure during en-masse retraction. All outcomes will be assessed as the difference between T0 at the start of retraction and T1 after complete space closure.

Secondary outcomes: is to monitor the changes in the anterior teeth position (torque and vertical position), molar rotation, anchorage loss, and pain associated with the different methods used for retraction.

E] Participant timeline:

1. The principle investigator will screen the potential patients through careful clinical examination of patients at the orthodontic department, Faculty of Oral and Dental Medicine, Future University.
2. All recruited patients should fulfil the previously mentioned inclusion and exclusion criteria.
3. Every participant will be asked to sign an informed consent before the beginning of the study.
4. After patient's enrolment, each participant will be asked for pre-intervention records to ensure proper diagnosis.

5. The principle investigator will randomly allocate the patients to one of the intervention groups.
6. Anchorage will be secured by placement of miniscrew, followed by extraction of the first premolar.
7. Active intervention will begin after proper levelling and alignment of the upper arch.
8. The principle investigator will take pre-retraction records for every participant T0.
9. In Friction mechanics group, Power chain is used for anterior segment retraction while in Frictionless group, T-loop is used for retraction.
10. Each patient will come every 4 weeks for follow up visit, for appliance activation and uptake of impression for interim records.
11. After complete space closure, the principle investigator will take post-retraction records for each participant T1.
12. Every patient will fill up a questionnaire regarding his experience during treatment.
13. The principle investigator will continue the normal treatment and achieve proper finishing for every patient after the end of the study.

E] Sample size calculation:

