Blinding of the operators: Blinding will not be possible for the operators during the application interventions and during the follow up visits. The principal operator is responsible for assigning subjects to interventions according to the concealed allocation, appliance activation at follow up visits, dental impressions and acquisition of dental casts.

Blinding of the outcome assessors: It is a single blinded study, therefore, only the outcome assessors will be blind. The patients name will be sealed from pre and post radiographs and study models. Then two assessors will carry out, blindly and independently, the measurements and analysis of the study.

III) Data collection, management and analysis:

A] Data collection methods:

Primary outcome:

1. Retraction rate: to assess the antero-posterior movement of anterior teeth and first molars, the principle investigator will take study models for every participant monthly during the follow up visits. Then, The models will be digitalized and the landmarks, reference lines and planes will be identified on the pre, interim and post-retraction digital dental models for measurements reading.

Secondary outcomes

1. Anchorage loss: will be accessed by the principal investigator via digitalized dental models taken before and after the completion of retraction by identifying the landmarks, reference lines and planes, then will interpret the measurements in millimeters.

2. Molar Rotation: will be accessed by the principal investigator via digitalized dental models. These records will be taken before and after the completion of retraction by identifying the landmarks, reference lines and planes, then will interpret the measurements of the angles in degrees.

3. Pain: Each patient will fill a questionnaire regarding his treatment experience in a VAS scoring from 1-10. The questionnaire will include several questions related to oral hygiene, pain and discomfort experienced throughout the trial.

4. Anterior teeth torque, extrusion/intrusion: will be accessed by the principle investigator via lateral cephalometric radiographs taken before and after the completion of retraction. The principal investigator will identify the landmarks, reference lines and planes, then will interpret the measurements in degrees and millimeters.

B] Data management:

A colleague outside the research team will enter the data and organize it in excel sheets in the computer of the orthodontic department.

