A] Data Monitoring: An independent Data Monitoring Committee (DMC) will monitor the results of the study. The Committee will include the trial's supervisors, who will periodically review the trial data and identify the need for any adjustments or modifications during the study.

B] Interim Analysis: no interim analysis will be performed during the study.

C] Harm: The main operator will document and report any harms or unwanted effects during the study intervention to the trial supervisors. Also, any unpleasant experience will be reported by the patient in the final questionnaire at the end of the retraction. The main operator will be responsible for the management of any adverse effects or unfavorable side effects resulting from the appliance.

D] Auditing: The supervisor will follow up and review the different interventions and resulting data. And he will periodically follow up the trial progress including recruitment of patients, allocation of participants to study groups; adherence to interventions and reporting of harms. A meeting with the senior supervisor will be set every 3 months to monitor the progress of the study and the need for any adjustments.

V) Ethics and dissemination:

A] Research Ethics Approval:

The Ethical committee in Future University, Egypt will review the protocol before they approve it. The research Ethics committee will evaluate the different interventions of the study to ensure its ethical validity and the potential benefits to the participants.

B] Protocol amendments:

The main investigator will be responsible to complete a formal amendment in case of any modifications or adjustments to protocol that may affect the conduct of the

study, as changes in the study design or intervention procedures. The Orthodontics department, Faculty of Oral and Dental Medicine, Future University and the Ethics Committee will approve such amendment before proceeding in the study.

C] Consent:

The main investigator will be in charge for detailed explanation and elaboration of the different steps of the study interventions for each patient. Then will ask every participant to sign a written consent before they begin treatment. The consent will be written in Arabic.

D] Confidentiality:

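### The only scheduled pain collection is a recall questionnaire after space closure: its window does not match the objective of pain during retraction, and without a T0 score the plan's T0-T1 rule cannot be applied to pain

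*Combined protocol and SAP*

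**What the plan says.** All references are to the combined protocol and SAP.

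- **Objective** (Objectives of the study, secondary objectives): "Assessing the amount of anchorage loss, root resorption, pain and discomfort during retraction".
- **Instrument** (outcome table under Aim of the study): "Pain scoring sheets given to patients", scored on a VAS from 1 to 10. The table gives no time points.
- **Collection** (III, A] Data collection methods, Pain): "Each patient will fill a questionnaire regarding his treatment experience in a VAS scoring from 1-10". The next sentence sets the period covered: "The questionnaire will include several questions related to oral hygiene, pain and discomfort experienced throughout the trial".
- **Timing.** C] Interventions, under Post-retraction Questionnaire: "The patients of both groups will be asked to fill in questionnaires regarding their experience with their allocated technique". E] Participant timeline, item 12, directly after the T1 records of item 11: "Every patient will fill up a questionnaire regarding his experience during treatment". IV, C] Harm: "any unpleasant experience will be reported by the patient in the final questionnaire at the end of the retraction".
- **Outcome rule** (D] Outcomes): "All outcomes will be assessed as the difference between T0 at the start of retraction and T1 after complete space closure". The same section lists pain among the secondary outcomes.
- **Analysis** (III, C] Statistical Analysis): a comparison of values before and after treatment within each group, and a separate item on patient acceptance of the two techniques.

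**The concern.** The objective asks how much pain each type of mechanics causes while teeth are being retracted. A questionnaire completed once the space is closed, looking back over the whole trial, measures something else: a remembered summary that mixes pain from steps common to both arms with pain from the mechanics being compared.

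The questionnaire is tied to closure and not to a fixed time. The trial asks whether one arm closes faster, so the length of recall depends on the primary outcome. If the arms do differ in speed, a difference in remembered pain could partly reflect different recall periods. Patients are not blinded (II, D] Blinding), so a long look-back is also open to expectation.

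Finally, the plan states a T0-T1 rule for every outcome but lists no T0 pain score. As written, the analysis of pain cannot be carried out.

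**Working it through.** **1. Is a pain score scheduled anywhere other than after closure?**

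| Occasion | What the plan lists | Pain score listed? |
|---|---|---|
| T0 (C] Interventions, pre-intervention records) | Lateral cephalogram; impressions and scanned models | No |
| 4-weekly visits (C] Interventions, Follow up visits; timeline item 10) | Miniscrew stability, reactivation, impressions | No |
| After closure (timeline items 11-12) | T1 records, then the questionnaire | Yes |
| Not timed (outcome table) | Pain scoring sheets | Unspecified |

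**2. Does the recall window match the objective?** In the timeline, allocation is item 5, miniscrew placement and extraction item 6, levelling and alignment item 7, and T0 item 8. II, C] Implementation confirms that allocation precedes levelling. A question about the whole trial therefore covers items 5 to 11. The objective covers only the period from T0 to closure.

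**3. Can the T0-T1 rule be applied?** The rule needs a T0 value and a T1 value. Step 1 finds no T0 pain value, so neither the difference nor the within-group before-and-after test can be computed for pain. This needs no assumption about numbers.

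**4. How far could recall length differ by arm?** The documents give neither the space to be closed nor the rate by arm, so these values are assumptions. Look-back to first activation = space / rate.

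| Assumed rates (mm/month) | 5 mm of space | 7 mm of space | Difference between arms |
|---|---|---|---|
| 0.7 vs 1.0 | 7.1 vs 5.0 months | 10.0 vs 7.0 months | 2.1 to 3.0 months |
| 0.6 vs 0.8 | 8.3 vs 6.2 months | 11.7 vs 8.8 months | 2.1 to 2.9 months |
| 0.5 vs 1.5 | 10.0 vs 3.3 months | 14.0 vs 4.7 months | 6.7 to 9.3 months |
| 1.0 vs 1.0 | 5.0 vs 5.0 months | 7.0 vs 7.0 months | 0 |

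In relative terms, assume 7 mm, a slower arm at 0.7 to 1.0 mm per 4 weeks, and the other arm 30% faster.

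- Slower arm: 4 × 7 / 1.0 = 28 weeks to 4 × 7 / 0.7 = 40 weeks.
- Faster arm: 28 / 1.3 = 21.5 weeks to 40 / 1.3 = 30.8 weeks.
- Retraction alone: 1 - 1/1.3 = 23% shorter.
- Whole trial, with an assumed 12 to 24 weeks of levelling common to both arms: smallest (28 - 21.5) / (28 + 24) = 12%; largest (40 - 30.8) / (40 + 12) = 18%.

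The wording of the questionnaire points to the whole-trial window, hence 12-18% on these assumptions.

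**5. The plan's own figure.** No calculation is given for pain. The sample size of 10 per group (SD 0.76, difference 1.0, two-sided 0.05 assumed, power 0.8) reproduces by the normal approximation, and the exact t calculation gives power 0.795. Nothing here changes it.

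**The case against.** **The sheets may be meant for repeated use.** The outcome table speaks of sheets in the plural, the Harm section of a final questionnaire, and the pain paragraph gives no timing. The figure in D] Outcomes was not available for this check. A reader might infer that the plan fixes pain scoring at exactly one occasion; the documents do not say so. What stands is that no other occasion is scheduled in the text. If repeated scoring was intended, the schedule still has to be written.

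**The T0-T1 conflict may be only wording.** The rule sits in the paragraph on the primary outcome, and a randomised comparison of a post-retraction score needs no baseline. That is fair, and exempting pain would remove the contradiction. It would not align the recall window with the objective.

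**Recall is not plainly biased.** Both arms are reactivated every 4 weeks and both answer at the end of retraction, so time since the last activation is similar. Only the distance to earlier pain differs, and only if speeds differ. Treatment length could also be counted as part of each technique's effect on the patient's experience. A reader might infer that the comparison is biased in a known direction or by a known amount; neither can be derived from the documents.

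**The precision gain is not established.** A reader might average seven scores with correlation 0.5, obtain a variance factor of (1 + 6 × 0.5) / 7 = 0.571, take its square root, 0.756, and claim a detectable difference 24% smaller. The correlation is assumed, and the step treats a global recalled rating as having the variance of a single visit's score. A common cut-off visit would also reduce the number of scores. The case for repeated sheets does not rest on this.

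**Repeated sheets are imperfect.** They still rely on recall over 4 weeks by unblinded patients, and T0 follows extraction, miniscrew placement and levelling. Both points stand as limits of the fix.

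**Conclusion.** The point holds on the text in two respects without any numerical assumption: the scheduled recall window is wider than the objective, and the T0-T1 rule cannot be applied to pain. Both rest on reading the schedule as written, with the pain sheets left untimed.

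The third respect is conditional. Recall length differs by arm only if closure speed differs. The illustrative differences (2.1-3.0 months at 0.7 versus 1.0 mm per month; a whole-trial window 12-18% shorter for a 30% faster arm) rest on assumed space, rates and levelling time. They describe the recall period and say nothing about the size of any error in the pain comparison.

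Pain is a secondary outcome, so the primary analysis and the sample size are untouched. This is an inexpensive improvement that should be made, with medium confidence.

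**What to change.** **Preferred.** State the time points in the outcome table and in the data collection section. Give the existing VAS sheet at T0 and at each existing 4-week visit, asking about pain since the last activation. At T0 no retraction activation has occurred, so specify a look-back of matching length there. Compare arms either on the per-patient mean up to a visit common to both arms, chosen in advance, or with a mixed model adjusted for the T0 score. A T0 value also makes the stated T0-T1 difference computable. Keep the final questionnaire for patient acceptance.

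**If repeated scores are not collected.** Exempt pain from the T0-T1 rule and from the within-group before-and-after test. Define it as a recalled whole-treatment score, compare it between the two independent groups, and report it under that label and not as pain during retraction.

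**Cost.** One short form per existing visit, data entry, and a small burden on patients. No new visits or staff are needed and treatment does not change. Recall over 4 weeks by unblinded patients remains, and T0 is not a treatment-free baseline.
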